The study will enroll participants to complete a brief open-label clinical trial of a probiotic dietary supplement. Individuals who provide informed consent and are eligible for participation will attend three study visits. At Visit 1, the research team will collect data on demographics, substance use, and medical history. Eligibility will be determined using the criteria listed below. Blood samples will be taken by a licensed healthcare provider. Eligible participants will complete a one-hour magnetic resonance imaging (MRI) scan, to occur on a separate day due to MRI scheduling constraints. Participants will receive a 30-day supply of the probiotic supplement with dosing and storage instructions. Participants will be instructed to take the standard dosage of 2 probiotic capsules per day. Participants will be asked to respond to a daily query from the research team confirming that they have taken their daily probiotic dose. Visit 2 will be scheduled 15 days (plus or minus 5 days) after the initiation of the probiotic supplement. The research team will collect blood samples and assess alcohol consumption since Visit 1, protocol adherence, and potential side effects. Participants will attend Visit 3 upon completion of the probiotic supplement, to occur 30 days (plus or minus 5 days) after initiation. Data will be collected as described for Visit 2, plus participants will complete a final one-hour MRI scan. Visit 4 will take place 1-10 months after completion of the study probiotic as a "washout" time point. A blood sample and substance use assessment will be collected at Visit 4. Appointments will take place at the Center for Alcohol and Addiction Studies lab space in the School of Public Health, and MRI scans will be conducted at Brown's Magnetic Resonance Imaging Facility (MRF).

Data to be collected at each session is described below.

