- Visit 1 (Baseline Screening & MRI): Breath alcohol content (BrAC) will be measured using a handheld digital sensor to confirm BrAC of .00 g% at the time informed consent is obtained. Age, weight, pregnancy status, urine drug metabolites, recent alcohol use, treatment-seeking status, MRI safety/compatibility, safety for blood draw, basic medical history, and medication use will be assessed per Eligibility Criteria listed in Section 4. The research team will check the individual's state-issued photo ID to verify age and identity. Height and weight will be measured using a standard scale. Urine samples will be collected to test for presence of drug metabolites. Urine samples from participants who are able to become pregnant will be tested for pregnancy hormones. Basic demographic information, social history, and health-related data will be collected on questionnaires. Questionnaires on alcohol use and related symptoms (Alcohol Use Disorders Identification Test; AUDIT) will be administered. Blood samples will be taken for testing of biomarkers per the research aims. The Timeline Followback (TLFB) measure will be used to assess alcohol use in the past 30 days. Current or recent seeking of treatment for alcohol or drug use will be assessed. Participants will be interviewed for history of major medical conditions and current medication usage. Because it is necessary to confirm eligibility prior to MRI scanning and because advance notice is needed for MRI scheduling, participants will be asked to return on a separate day to complete a one-hour MRI scan of the brain at Brown's MRI Research Facility. Participants who are able to become pregnant will be given a urine pregnancy test prior to MRI scanning. BrAC of .00 g% will be confirmed prior to the MRI scan. Eligible participants will be given a 30-day supply of the probiotic supplement with dosing and storage instructions. The research team will collect contact information and request permission to send daily emails to confirm participants' adherence to the study protocol.
- Visit 2: Participants will complete questionnaires on side effects and adherence to the study protocol. Blood samples will be taken for testing of biomarkers. BrAC of .00 g% will be confirmed prior to study procedures.

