- Visit 3 (Day 30 of Probiotic Intervention): The TLFB will be used to assess alcohol use since Visit 1. Side effects, adherence data, and blood samples will be collected as before. Participants who are able to become pregnant will be given a urine pregnancy test prior to MRI scanning. BrAC of .00 g% will be confirmed prior to the MRI scan. Participants will complete a one-hour MRI scan. They will be debriefed about the study and given the opportunity to ask questions at study completion.

v. 6/5/2020 Page **6** of **19** 

 Visit 4: A post-assessment visit will be conducted 1 to 10 months after completion of the probiotic. The Timeline Followback will be used to assess alcohol use in the past 30 days. A blood sample will be taken.

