## 6. Compensation / Reimbursement

Participants will be compensated for their time and effort as follows: \$50 for Visit 1 screening (approximately 2.5 hours) and \$50 for Visit 1 MRI (approximately 1.75 hours); \$30 for Visit 2 (approximately 1.5 hours); \$80 for Visit 3 (approximately 3 hours); \$1 per day for each day the participant responds to emails about adherence (maximum \$30); \$40 for Visit 4 (approximately 1.5 hours). Participants found not eligible to complete the study at Visit 1 will be given compensation prorated at \$20/hour. Participants will be offered reimbursement for parking and/or transportation as needed. Payments will be made by electronic gift card, specifically an Amazon gift card. The compensation rate of approximately \$20/hour is appropriate for the time, effort, and activities involved in participation. Participants will be paid at the completion of each visit. For the daily response compensation, participants will be paid at the end of the 30-day period for the total of days that they responded.

- 7. Potential Research Risks / Discomforts to Participants. In order to approve the research, the IRB must consider the risks posed to participants by the research and any efforts to mitigate those risks. The IRB needs to determine that the risks have been both minimized and are reasonable in relation to the anticipated benefits to participants, as well as to the importance of the knowledge that may be gained. The IRB will also consider whether the informed consent process provides potential participants with an accurate and fair description of the risks or discomforts.
- 1. Risk of side effects from probiotic supplementation: The study will utilize a commercially available probiotic supplement product (Seed DS-01™ Daily Synbiotic) that has an excellent safety and tolerability profile. The most common side effects of probiotics are abdominal bloating and/or gas, which typically dissipate after the first few days of use. The Seed DS-01™ Daily Synbiotic undergoes rigorous quality control testing for contaminants (e.g., heavy metals, pesticides) and allergens (e.g., nuts, gluten, milk) and is the subject of ongoing independent clinical trials for irritable bowel syndrome and post-antibiotic recovery. The product is vegan, preservative-free, and free of common allergens (soy, dairy, gluten). Probiotic supplements are not regulated by the FDA or subject to IND requirements.

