- 7. Risk of adverse reaction to the probiotic supplement: In the unlikely event that a participant reports adverse reaction to the probiotic beyond the mild side effects noted in #1 above, the participant will be instructed to discontinue the probiotic and will be withdrawn from the study.

Standard of Care: There is no established "standard of care" for healthy heavy drinkers who are not seeking treatment. The probiotic supplement does not replace or otherwise alter any clinical care that participants would receive. At the conclusion of the study, participants will be given an NIAAA pamphlet on the risks of heavy drinking.

v. 6/5/2020 Page **9** of **19** 

DSMP/DSMB: The DSMP is attached and contains information on the DSMB.

8. Potential Benefits of the Research. NOTE: Compensation for participation is not a benefit and should not be included in this section. In order to approve this research, the IRB must determine that the potential benefits to research participants are reasonable in relation to the potential risks. Very often, research at Brown does not include potential direct benefits to participants, but may only benefit society as a whole by helping researchers.

Some individuals experience a noticeable benefit in health when using probiotics. Many subjects in this study are unlikely to benefit directly from participation. Benefits to society are expected to accrue through generation of scientific knowledge about effects of probiotics on inflammation in heavy drinkers.

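### Side effects are first asked about at day 10 to 20, with no pre-dose symptom form and no stated recall period, so early bloating and gas may be under-reported and background symptoms cannot be told apart from product effects

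*Combined protocol and SAP*

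**What the plan says.** **Expected time course.** Protocol Part III, section 7, item 1: "The most common side effects of probiotics are abdominal bloating and/or gas, which typically dissipate after the first few days of use".

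**When side effects are asked about.** Section 3, overview: "Visit 2 will be scheduled 15 days (plus or minus 5 days) after the initiation of the probiotic supplement". For that visit the overview adds: "The research team will collect blood samples and assess alcohol consumption since Visit 1, protocol adherence, and potential side effects". The Visit 2 list reads "Participants will complete questionnaires on side effects and adherence to the study protocol", and the Visit 3 list "Side effects, adherence data, and blood samples will be collected as before". Visit 4 lists alcohol use and a blood sample only.

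**What precedes the first capsule.** The Visit 1 list is detailed (breath alcohol, urine tests, AUDIT, Timeline Followback, medical history, medication). The nearest entry to a symptom measure is "Basic demographic information, social history, and health-related data will be collected on questionnaires".

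**Contact between visits.** "Participants will be asked to respond to a daily query from the research team confirming that they have taken their daily probiotic dose". No symptom item is described.

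**Unscheduled reports.** Section 7, item 7 sets out what follows "In the unlikely event that a participant reports adverse reaction to the probiotic beyond the mild side effects noted in #1 above". The same section refers to an attached data and safety monitoring plan, which is not in the text available for review.

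**Aim and analysis.** Aim 3 concerns acceptability and feasibility in non-treatment-seeking heavy drinkers. The SAP covers plasma biomarkers and describes no analysis of side effects. It reports 16 starters, 14 who completed the course and two lost to follow-up before completing it.

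**The concern.** The effects that the protocol expects are early and short-lived, but the first scheduled question about them comes in the second or third week. Unless the questionnaire looks back over the whole period, symptoms that have already gone may not be recorded. If it does look back, the record depends on memory of mild symptoms.

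The second problem is attribution. The trial is open-label with one arm, so a participant's own pre-dose state is the only internal comparator. Biomarkers, brain imaging and alcohol use each have a baseline; symptoms, as described, do not. Someone who had bloating or gas before starting cannot be distinguished from someone who developed it on the product.

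At stake is the side-effect information that the pilot passes to the full-scale work it is meant to inform. Aim 3 does not name tolerability, but side effects bear on whether people find a supplement acceptable. With 16 starters, one misclassified participant moves the proportion by 1/16 = 6.25 percentage points.

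**Working it through.** **1. Timing, reproduced from section 3.** Visit 2: 15 − 5 = day 10 to 15 + 5 = day 20. Visit 3: 30 − 5 = day 25 to 30 + 5 = day 35. The first scheduled enquiry is therefore at day 10 to 20.

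**2. Gap between typical resolution and first enquiry.** The protocol puts no number on the first few days; 3 to 7 days is assumed here. Gap = day of Visit 2 − day of resolution.

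| Assumed resolution | Visit 2 at day 10 | Visit 2 at day 20 |
|---|---|---|
| day 3 | 7 days | 17 days |
| day 5 | 5 days | 15 days |
| day 7 | 3 days | 13 days |

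The gap is 3 to 17 days and is positive throughout the assumed range.

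**3. Recall period.** In the overview's description of Visit 2, the reference back to Visit 1 is attached to alcohol consumption. No period is attached to side effects there or in the visit lists.

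**4. Can size or direction be fixed?** As an illustration only, let p be the true proportion with an early product symptom, r the share of these still reported at Visit 2, and b the proportion who would report a background symptom. With independence, the proportion reporting is 1 − (1 − p·r)(1 − b). All three inputs are assumed; the documents give none. Take p = 0.30, or 16 × 0.30 = 4.8 expected true cases.

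| r | b | Proportion reporting | Expected reports of 16 |
|---|---|---|---|
| 1.00 | 0 | 1 − 0.70 × 1 = 0.30 | 4.8 (no error) |
| 0.25 | 0 | 1 − 0.925 × 1 = 0.075 | 1.2 (under-count) |
| 1.00 | 0.20 | 1 − 0.70 × 0.80 = 0.44 | 7.0 (over-count) |
| 0.50 | 0.20 | 1 − 0.85 × 0.80 = 0.32 | 5.1 (near-cancelling) |

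The two errors cancel exactly when b = 1 − (1 − p)/(1 − p·r). With p = 0.30 and r = 0.50, b = 1 − 0.70/0.85 = 0.176. Depending on values that the documents do not give, the net error can be negative, positive or close to zero.

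**5. Losses.** 2/16 = 12.5% were lost before completing the course. The SAP does not say whether this was before or after Visit 2, so side-effect data may be missing for none, one or both. Two is the upper limit.

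There is no power or sample-size figure to reproduce: the target of 15 completers is justified only as a pilot size.

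**The case against.** The strongest reply is that the questionnaire itself cannot be seen. If it asks about everything since the first capsule, early symptoms are covered at the price of a recall of 10 to 20 days. If it asks for new or worsened symptoms, attribution to background is reduced. The attached safety monitoring plan might also describe further collection. This stands, and it is why the point is about risk. It does not remove the gap: a question about new or worse symptoms, asked only afterwards, still relies on the participant's memory of the earlier state.

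Three stronger readings are tempting and unsupported:

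- *That side effects are shown to be miscounted in both directions.* Both directions are possible, but neither the sizes nor the net sign can be derived, and the errors may nearly cancel.
- *That anyone who stops early leaves no side-effect record.* Section 7, item 7 provides for reports outside the schedule, although the action stated there concerns reactions beyond the mild expected ones. Stopping capsules is also not the same as missing Visit 2.
- *That the two losses show missing early data.* Neither their timing relative to Visit 2 nor a reason is given.

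It is also fair to say that the effects are mild, known and self-limiting, that participants are described as healthy, that adherence and retention inform Aim 3 as well, and that no analysis in the SAP uses side-effect counts. This limits the importance of the point. The low cost of the remedy still makes it worth adopting. Daily symptom questions can prompt reports; that is a real cost of the change.

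**Conclusion.** The point holds as a weakness in the described schedule. The first scheduled side-effect enquiry falls at day 10 to 20, after the protocol's own expected resolution of bloating and gas: by 3 to 17 days if the first few days means 3 to 7. No pre-dose symptom form and no recall period are described, and the daily contact checks adherence only. Early transient symptoms are at risk of under-reporting. With no control arm, nothing described allows background symptoms to be separated from product effects.

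The size and net direction of any error cannot be determined from the documents, and the proportions in the illustration are assumptions. Side-effect data may be missing for up to two of 16 starters. The bearing on Aim 3 is by inference. A reader might treat tolerability as a defined part of that aim, but the text does not name it there. The primary biomarker analysis is unaffected.

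**What to change.** For any further enrolment and for the follow-on trial:

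1. Give the same side-effect questionnaire at Visit 1, before the first capsule.
2. State its recall period, and have the Visit 2 form ask about the whole period since the first capsule.
3. Report symptoms that are new or worse than at Visit 1.
4. Add one brief symptom item to the existing daily email for at least days 1-10, and report results from it alongside the visit questionnaires.

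The cost is one extra form, one extra email item and a minor IRB amendment. Participants bear slightly more burden, and the daily item may prompt reports and raise the recorded count of mild early symptoms. Sample size and study visits do not change.

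The SAP describes the cohort in the past tense, so a pre-dose measure cannot be added for those participants. For them, report the lack of a pre-dose symptom measure and of early symptom capture as a limitation of the side-effect data, and state whether the two lost participants attended Visit 2.

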## PART IV. INFORMED CONSENT

Informed consent is a *process*, not just a form. The IRB must ensure the informed consent process clearly discloses and facilitates the understanding of all information needed to make an informed decision to participate while promoting the voluntariness of participation.

Please use the Brown consent / assent templates and related guidance on the HRPP Forms & Templates page to develop your consent forms.

## 1. Describe the informed consent process, including:

Informed consent will be obtained at Visit 1. BrAC of .00 g% will be confirmed at the time that consent is obtained. The nature of the study will be described verbally and in writing. Potential participants will be informed that study participation is voluntary and that they have the right to terminate study procedures at any time. Participants will be informed that the alternative is to not participate. Written informed consent will be obtained by the PI or trained Research Assistant. The Research Assistant will receive one-on-one training from the PI in consent procedures. The names and contact information of the PI ([name]) and study staff will be provided on the consent document in case questions arise. Participants will receive a copy of the signed consent document, and the original form will be kept in a locked filing cabinet.

### 2. Facilitate Understanding

Participants will be encouraged to ask questions to clarify the nature of the study and to ensure understanding. Participants who decide to withdraw from the study at any point prior to completion will be paid for their participation up to that point.

#### 3. Documentation

Participants will indicate informed consent by signing the consent form.

#### 4. Additional Considerations

v. 6/5/2020 Page **10** of **19** 

#### STATISTICAL ANALYSIS PLAN

The goal of this analysis was to observe the effect of the probiotic on plasma concentrations of sCD14, sCD163, LBP, IL-6, IL-8, IL-10, MCP-1, and TNF-α. Of the 16 eligible participants who initiated the probiotic, 14 participants completed the probiotic course, and two were lost to follow-up prior to completion. Ten participants returned after the washout period for Visit 4. Descriptive statistics were obtained on demographic characteristics and drinking history. All collected datapoints were considered for analysis regardless of probiotic completion or loss to follow-up. Biomarker concentrations greater than three standard deviations from the mean were excluded to limit the impact of statistical outliers on the analysis. Regarding undetectable biomarker values, sCD14 had 3.7% missing data (n=2), IL-6 had 35% missing data (n=19), IL-10 had 5.6% missing data (n=3), LBP had 1.8% missing data (n=1), and MCP-1 had 5.6% missing data (n=3). There were no undetectable biomarker values for IL-8, sCD163, or TNF-α. Regarding outlier exclusions, IL-6 had one outlier value, IL-8 had two outlier values, LBP had one outlier value, sCD163 had one outlier value, and TNF-α had one outlier value. Distributions for sCD14, IL-10, and MCP had no outlier values.

Linear mixed models were used to assess changes in biomarkers over the study period. Models included the effect of alcohol use variables (assessed at Visit 1, Visit 3, and Visit 4) as time-varying covariates, specifically, number of heavy drinking days, total number of drinking days in, total number of standard drinks, and days since last drink. Self-reported alcohol use variables were treated as continuous. Self-reported drinking variables were assessed for collinearity and included in the final model if they met an acceptable variance inflation factor (VIF) <10. Total number of standard drinks was dropped from the final model due to high VIF. Despite prior evidence for sex effects on alcohol consumption and its impacts, there were too few females to test for this effect, and sex was not included in models. Models were specified to identify participant as the subject variable and visit number (1, 3, and 4) as the repeated measure, and with fixed slope and intercept. An autoregressive variance-covariance structure was selected for optimal model fit based on the Akaike Information Criterion (AIC). In the primary model (Model 1), the trajectory of biomarker concentrations before, during, and after probiotic use were examined, with alcohol variables (number of heavy drinking days, number of drinking days, and days since last drinks) included as time-varying covariates. In Model 1, biomarker

concentrations below the threshold of detectability were treated as missing data in analyses. Of note, maximum likelihood estimation as applied in the linear mixed model approach is able to handle missing data without excluding cases listwise or imputing data, thus making full use of the available data and minimizing bias in parameter estimates (Baraldi & Enders, 2010). To assess for non-linear changes in biomarker concentrations, a secondary model (Model 2) was tested to include a quadratic effect of time for the biomarker outcomes. Finally, a sensitivity analysis model (Model 3) was tested to assess for the effect of data missing at random. In Model 3, data below the detectability threshold of the assay (i.e., missing) were imputed at half the value of the threshold per the manufacturer. All analyses in this paper were conducted using SAS software, version 9.4 for Windows (SAS Institute, Cary NC.)

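### Six biomarker values in five of the eight markers are excluded for their size alone, and no described model keeps them

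*Combined protocol and SAP*

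**What the plan says.** The first paragraph of the Statistical Analysis Plan sets the rule: "Biomarker concentrations greater than three standard deviations from the mean were excluded to limit the impact of statistical outliers on the analysis". It then counts the exclusions: "IL-6 had one outlier value, IL-8 had two outlier values, LBP had one outlier value, sCD163 had one outlier value", plus one for TNF-α. For the remaining markers it says "Distributions for sCD14, IL-10, and MCP had no outlier values". Undetectable values are counted separately.

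The second paragraph describes three models.

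- Model 1 sets undetectable values to missing. It uses "visit number (1, 3, and 4) as the repeated measure, and with fixed slope and intercept".
- For curvature, "a secondary model (Model 2) was tested to include a quadratic effect of time for the biomarker outcomes".
- Model 3 is the only one labelled a sensitivity analysis. In it, "data below the detectability threshold of the assay (i.e., missing) were imputed at half the value of the threshold".

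Outliers are not mentioned in the description of any model.

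**The concern.** The rule deletes observed outcomes because of their own value. That differs from a missed visit or a result below the assay limit. The plan's argument that maximum likelihood copes with missing data does not cover it, because whether a value is absent depends on the value itself.

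The plan tests its handling of the lower tail (Model 3) but not of the values removed as extreme. With at most 16 people, a single extreme value can carry real weight in a slope. If the removed values are high, losing one at Visit 1 flattens an apparent fall, and losing one at Visit 4 steepens it. The effect on these markers is the stated goal of the analysis, and five of the eight are affected.

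**Working it through.** **1. Count of exclusions.** From the first paragraph of the Statistical Analysis Plan: 1 + 2 + 1 + 1 + 1 = 6 values in five markers. IL-8, sCD163 and TNF-α had no undetectable results, so their 2 + 1 + 1 = 4 outliers are certainly detected values. For IL-6 and LBP the same follows from the separate count of undetectable values.

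**2. Samples per marker (inferred).** The printed undetectable percentages fit 54 samples: 2/54 = 3.7%, 19/54 = 35.2%, 3/54 = 5.6%, and 1/54 = 1.85%, printed as 1.8%. Neither 53 nor 55 fits: 2/53 = 3.77% and 2/55 = 3.64%, against 3.7% printed.

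**3. Share removed.** Undetectable values total 2 + 19 + 3 + 1 + 3 = 28.
- All eight markers: 8 × 54 − 28 = 404 detected values, and 6/404 = 1.5%.
- The five affected markers: 35 + 54 + 53 + 54 + 54 = 250, and 6/250 = 2.4%.

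**4. How many left the models.** The models use Visits 1, 3 and 4. Sixteen people started, 14 completed, and "Ten participants returned after the washout period for Visit 4". That gives about 16 + 14 + 10 = 40 samples per marker, if all 16 gave blood at Visit 1 and 14 at Visit 3. The surplus is 54 − 40 = 14. It would fit Visit 2, for which the protocol (Part III, Section 3) says "Blood samples will be taken for testing of biomarkers. BrAC of .00 g% will be confirmed prior to study procedures". An outlier from Visit 2 would never have entered a model. Six is therefore an upper limit on the values the models lost.

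**5. What each model does with the six.**

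| Model | What is described | Outliers restored? |
|---|---|---|
| 1 | Undetectable values set to missing | Not described |
| 2 | Quadratic time added | Not described |
| 3 | Undetectable values set to half the threshold | Not described |

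**6. Leverage of one value (illustration only).** The documents give no biomarker values, so every input here is assumed:
- a linear slope over visits, coded 1, 3, 4 or 1, 2, 3;
- AR(1) correlation by visit order of 0.3, 0.5 or 0.7;
- nested attendance of 16/14/10;
- no covariates, and one value at +3 SD.

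The slope is the generalised least squares estimate, β = (XᵀV⁻¹X)⁻¹XᵀV⁻¹y. The shift is (slope without the value − slope with it) / SE of the slope with all values in. The person's other values are set either at the mean or at their conditional mean given the extreme one.

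| Deleted value | Shift in SE units |
|---|---|
| Visit 1 | +0.34 to +0.93 |
| Visit 3, person also seen at Visit 4 | −0.01 to −0.40 |
| Visit 3, person not seen at Visit 4 | −0.24 to −0.84 |
| Visit 4 | −0.31 to −0.90 |

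This does not represent IL-6. If its 35 detected values were spread evenly, about 16 × 35/54 = 10.4, 14 × 35/54 = 9.1 and 10 × 35/54 = 6.5 would remain at Visits 1, 3 and 4. Nor does it represent IL-8, which lost two values.

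**The case against.** The other side has good points. The rule, its purpose and the count per marker are all disclosed. The trial is a proof-of-concept pilot, and about 1.5% of detected values are involved. The plan is written in the past tense and refers to a paper that is not among these documents, so the visit and direction of each value may be reported there. All of this bears on how serious the point is. It does not supply a model that keeps the values. The statement that all collected datapoints were considered concerns completion of the course and loss to follow-up, and the exclusion rule comes after it.

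A reader might infer more than the documents support:

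- **That all six values were lost from the models.** Some may be Visit 2 values (working, step 4).
- **That the exclusions changed a finding, or favoured the probiotic.** No biomarker values, variances or slopes are given, and the plan states no significance level. Simulated rates of a change in significance move with the assumptions and are not evidence about this trial. The sign of any bias depends on the visit and direction of each value, which are not stated.
- **That the rule treats visits unequally.** If the mean and SD were taken within visit, the largest possible |z| in n values is (n − 1)/√n, which is 9/√10 = 2.85 at Visit 4, so no value there could be excluded. The plan does not say that limits were per visit, and pooling over visits is the more natural reading. This is a question for the authors, not a defect shown.

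**Conclusion.** The point stands as a gap in the sensitivity analysis. Six values in five of eight markers are excluded on size alone, and no described model shows what happens when they stay in. The count and the contents of the models come straight from the Statistical Analysis Plan. The 54 samples per marker, and the resulting 1.5% and 2.4%, are inferred.

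Under the assumed inputs, one deletion can move a slope by up to about 0.9 SE or hardly at all, depending on the visit and the person's other visits. That is enough to justify the check and not enough to say that any result is wrong. The change is worth making because it is cheap and affects how five trajectories are read.

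**What to change.** For IL-6, IL-8, LBP, sCD163 and TNF-α, re-run Models 1 to 3 with all detected values kept, leaving out only those with a documented assay or sample failure. Report these results beside the 3-SD-excluded ones. State the visit and direction of each excluded value, and whether the 3-SD limits were pooled over visits or set per visit. Describe any conclusion that differs between the two sets as dependent on the exclusion.

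A log-scale version is optional. If done, apply it to all five markers and do not choose marker by marker.

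The cost is 5 × 3 = 15 further model fits on existing data and one added table. Intervals in the all-values runs may be wider. If the log-scale option is taken, results read as ratios, and the 19 IL-6 values imputed at half the threshold would gain leverage in Model 3.

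### Primary Model 1 appears to fit one straight line through Visits 1, 3 and 4, so washout change enters the estimate, and no model names the on-treatment change (Visit 3 minus Visit 1)

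*Combined protocol and SAP*

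**What the plan says.** The Statistical Analysis Plan opens with its purpose: "The goal of this analysis was to observe the effect of the probiotic on plasma concentrations" of eight named markers. Its models are introduced with "Linear mixed models were used to assess changes in biomarkers over the study period", and the repeated structure is given as "visit number (1, 3, and 4) as the repeated measure, and with fixed slope and intercept". For primary Model 1, "the trajectory of biomarker concentrations before, during, and after probiotic use were examined", with drinking variables as time-varying covariates. Non-linear change is left to a further step: "a secondary model (Model 2) was tested to include a quadratic effect of time". Model 3 alters only the handling of undetectable values. No visit contrast is named in any model, and the plan does not say whether time is visit number, visit order or days.

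Protocol section 3 (Materials, Methods and Analysis) fixes when product is taken. "Participants will attend Visit 3 upon completion of the probiotic supplement", about 30 days after starting. "Visit 4 will take place 1-10 months after completion of the study probiotic". On attendance, the plan reports 16 who started, 14 who completed the course, and "Ten participants returned after the washout period for Visit 4".

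**The concern.** Visit 1 to Visit 3 is time on product, and Visit 3 to Visit 4 is time off it. A single slope across both equals the on-treatment change only if the three visit means lie on a straight line in the chosen time scale. A washout visit is scheduled precisely because they may not.

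The primary estimate would then depend partly on months without product, and the error can run either way. A real on-treatment fall that reverses is shrunk. A fall that arises only after stopping is partly credited to the on-treatment period. Aim 1 seeks proof of concept for benefit from taking the probiotic, so the headline number should describe the period in which it was taken.

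**Working it through.** The documents give no power, alpha or effect size, so there is no stated figure to reproduce. The check is algebraic.

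**Reading of Model 1.** With three visits, a visit factor already fits any pattern of visit means, so adding a by-visit quadratic to it would change nothing. A slope in Model 1 and a separate quadratic Model 2 make sense together only if Model 1 is linear in time. This is inference, not a statement in the plan.

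**Inputs from the plan.** 16 participants at Visit 1, 14 at Visit 3 and 10 at Visit 4; autoregressive covariance.

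**Assumptions.**
- Attendance: 10 participants have all three visits, 4 have Visits 1 and 3, and 2 have Visit 1 only.
- Visits are coded 1, 3, 4.
- AR(1) correlation between adjacent analysed visits is 0.5 or 0.7, with unit SD.
- Drinking covariates, undetectable values and outlier exclusions are ignored.

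**Formula.** Generalised least squares with intercept and slope: b = (Σ X′R⁻¹X)⁻¹ Σ X′R⁻¹μ. The implied Visit 1–3 change is slope × (3 − 1). Write D for Visit 3 minus Visit 1 and W for Visit 4 minus Visit 3. Then:

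- correlation 0.5: implied change = 0.792 D + 0.417 W
- correlation 0.7: implied change = 0.812 D + 0.376 W

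The implied change equals D only when W = (1 − 0.792)/0.417 × D = 0.50 D, that is, when the marker falls half as much again after stopping. Under full reversal W = −D, so the line keeps 0.792 − 0.417 = 0.375 of D, or 0.812 − 0.376 = 0.436 of D. For D = −0.8 SD these are falls of 0.30 and 0.35 SD.

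**Power.** Noncentral t, 22 df (assumed), two-sided 5%, noncentrality = implied change / SE. At correlation 0.5 / 0.7 the SE is 0.217 / 0.178 for the line and 0.263 / 0.205 for the direct contrast. Full reversal at 0.5: line 0.300/0.217 = 1.38, power 26%; contrast 0.800/0.263 = 3.04, power 83%.

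True on-treatment fall of 0.8 SD (except the last row). Ranges span the two correlations. The direct contrast recovers 0.80 SD with 83–96% power in every row but the last, where it correctly gives zero.

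| Visit 4 pattern | Fall implied by line (SD) | Power, line | Power, Model 2 quadratic term |
|---|---|---|---|
| Full reversal | 0.30–0.35 | 26–47% | 89–99% |
| Half reversal | 0.47–0.50 | 54–77% | 57–80% |
| Sustained | 0.63–0.65 | 80–94% | 19–29% |
| Further 0.4 SD fall | 0.80 (exact) | 94–99% | 5% (no curvature) |
| Further 0.8 SD fall | 0.95–0.97 (overstated) | 99% or more | 19–29% |
| No on-treatment change, Visit 4 lower by 0.8 SD | 0.30–0.33 (spurious) | 31–37% | 57–80% |

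**Sensitivity.**
- Equal-step coding: under full reversal the line implies 0.09–0.11 SD (power 8–11%), and the Model 2 term has 93–99.5%.
- Correlation 0 to 0.3, full reversal: line 0.20–0.26 SD (12–18%), contrast 55–70%, Model 2 term 59–76%.
- True fall of 0.5 SD, fully reversed: line 0.19–0.22 SD (13–22%), contrast 44–65%, Model 2 term 52–75%.
- Actual days, Visit 4 spread evenly over days 60 to 330, full reversal: the line runs from a 0.002 SD fall to a 0.06 SD rise. Model 2 is then no longer saturated and implies only a 0.12–0.28 SD fall. The text does not suggest this scale.
- Simulation (600 runs per setting, REML, variance and correlation estimated), full reversal: line 0.26–0.29 SD with 16–19% power, contrast 82–96%. The closed form is therefore generous to the line in this case.

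**The case against.** **The linear reading is inferred.** A fixed slope and intercept may mean only that there are no random effects, and a trajectory over three periods could describe a visit factor. This stands as a limit on certainty. If visit was a factor, the mixing disappears, but the plan would still name no contrast, and a by-visit Model 2 would be redundant.

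**Model 2 covers non-linearity.** Coded by visit, it is saturated: Visit 3 minus Visit 1 can be derived from it exactly. It also detects a full reversal slightly more often than the direct contrast does. So the plan as a whole is not blind to reversal. But Model 2 is secondary, its stated purpose is to test curvature, its linear coefficient alone is not Visit 3 minus Visit 1, and its power is low when the effect is sustained under coding 1, 3, 4.

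**The on-treatment change is not named as the target.** The plan also speaks of change over the whole study period. That is true, but its declared goal is the effect of the probiotic, which fits the period of use best.

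**The sizes rest on assumed inputs, and this is an uncontrolled pilot.** Both points stand. The power figures only compare models, and Visit 3 minus Visit 1 remains a within-person change, not proof of a probiotic effect.

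**The contrast can lose power.** With a sustained effect and correlation 0, the line has 62% and the contrast 55%. Under compound symmetry at 0.5–0.7 the figures are 87–98% and 83–96%. The line gains this while understating the change.

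**Conclusion.** The point holds, with medium confidence because Model 1's linearity is inferred. As best read, the primary model gives washout change a weight of about 0.38–0.42 in its implied on-treatment change (visits coded 1, 3, 4, AR(1) correlation 0.5–0.7). A fully reversed effect is more than halved, a sustained one is understated by about a fifth, and a late fall produces a spurious on-treatment fall. These sizes depend on the assumed coding, correlation, attendance pattern and Visit 4 pattern. The algebra behind them does not: one line recovers the on-treatment change only if the three means are collinear on the time scale used. The absence of a named Visit 3 minus Visit 1 contrast is plain from the text. This should be fixed; it does not invalidate the pilot.

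**What to change.** - State the time scale used in Models 1 and 2.
- Enter visit as a three-level factor in Model 1.
- For each biomarker, report Visit 3 minus Visit 1 with its confidence interval as the main estimate, and Visit 4 minus Visit 3 separately as the washout estimate.
- Keep the linear and quadratic fits as secondary descriptions.
- Name the type of autoregressive structure, and check one covariance structure that does not assume equally spaced visits.

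The cost is a change of wording and a re-run on existing data, with one more fixed-effect parameter, which Model 2 already spends. Power falls modestly in some sustained-effect settings. The plan is written in the past tense with attrition known, so the contrasts should be labelled post hoc if results have been seen; the change cannot restore prespecification.
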